#### **3.1.3.1.4. Onset Day of Each Local Reaction**

The onset day of each local reaction will be derived. Onset day is defined as the first day of reporting any severity.

For the onset day of each local reaction, if the participant reports changes in severity of the local reaction, only the first day of reporting that specific local reaction will be counted.

### 3.1.3.2. Systemic Events Within 7 Days After Vaccination

Systemic events, including fever, fatigue/tiredness, headache, vomiting, nausea, diarrhea, muscle pain, and joint pain, are reported from Day 1 through Day 7 after vaccination, where Day 1 is the day of vaccination with RSVpreF or placebo. The derivations for the systemic events as described below will be handled similarly to the way that local reactions are handled for the presence for each participant, severity level, duration, onset day, and presence of systemic event on each and any day.

1. Presence (yes or no) of each systemic event on any day (Day 1 through Day 7) after each dose.
2. Presence (yes or no) of any systemic event on any day (Day 1 through Day 7) after each dose.
3. Maximum severity of each systemic event on any day (Day 1 through Day 7) after each dose.
4. Maximum severity of any systemic event on any day (Day 1 through Day 7) after each dose.
5. Duration of each systemic event after each dose.
6. Onset day of each systemic event after each dose.

The above items 1 through 4 will also be derived for “after any dose.” This is for Substudy B only.

The grading scale for systemic events is provided in the protocol. However, the derivation of severity of each systemic event on each day should be based on the maximum severity reported from the e-diary or AE CRF, if data are reported from both sources, or the e-diary alone if not reported from the AE CRF.

Fever is defined as a temperature of  $>100.4^{\circ}\text{F}$  ( $\geq38.0^{\circ}\text{C}$ ). The highest temperature for each day will be recorded in the e-diary. For reporting purposes, fever will be analyzed using the following temperature ranges:

- Mild ( $\geq38.0^{\circ}\text{C}$  to  $38.4^{\circ}\text{C}$  from the e-diary or mild grade from the AE CRF).
- Moderate ( $\geq38.4^{\circ}\text{C}$  to  $38.9^{\circ}\text{C}$  from the e-diary or moderate grade from the AE CRF).
- Severe ( $>38.9^{\circ}\text{C}$  to  $40.0^{\circ}\text{C}$  from the e-diary or severe grade from the AE CRF).
- Grade 4 ( $>40.0^{\circ}\text{C}$  from the e-diary or severe grade from the AE CRF, plus documented  $>40.0^{\circ}\text{C}$  via CRF query or other sources).

If a participant reports a fever (or severity of fever) by mistake, the correct temperature will be transcribed in a data handling memo to be included in the analysis, and the temperature that is confirmed as incorrect will not be included in the analysis.

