8.3.4.4. Temperature

A digital thermometer will be given to the participant with instructions on how to measure temperature at home. Temperature will be collected in the reactogenicity e-diary in the evening daily during the reactogenicity e-diary reporting period. It will also be collected at any time during the reactogenicity reporting period that fever is suspected.

Fever is defined as a temperature of $\geq 38.0^{\circ}\text{C}$ ($\geq 100.4^{\circ}\text{F}$). The highest temperature for each day will be recorded in the e-diary, where possible. Temperature will be measured and recorded to 1 decimal place. Temperatures recorded in degrees Fahrenheit will be

programmatically converted to degrees Celsius and then categorized during analysis as mild, moderate, or severe based on the intensity grading scale provided in Table 4.

In the event of a fever on the last day the diary was completed, temperature will be measured daily until the fever has resolved (1 day of temperature less than 38.0°C [100.4°F]) in order to collect a stop date in the CRF.

If a fever of >38.9°C (>102.0°F) is reported in the e-diary, a telephone contact should occur to ascertain further details and determine whether a site visit is clinically indicated.

Only an investigator or qualified designee is able to classify a participant's fever as Grade 4, after clinical evaluation of the participant, documentation from another medically qualified source (eg, emergency room or hospital record), or contact with the participant. Grade 4 fevers will be collected on the AE CRF and assessed by the investigator using the AE intensity grading scale as detailed in [Section 10.2.3](#).

Table 4. Ranges for Fever

	Mild Grade 1	Moderate Grade 2	Severe Grade 3	Grade 4 ^a
Fever	≥38.0°C to 38.4°C (100.4-101.1°F)	>38.4°C to 38.9°C (101.2-102.0°F)	>38.9°C to 40.0°C (102.1-104.0°F)	>40.0°C (>104.0°F)

a. Only an investigator or qualified designee is able to classify a participant's fever as Grade 4, after clinical evaluation of the participant, documentation from another medically qualified source (eg, emergency room or hospital record), or contact with the participant. Grade 4 fevers will be collected on the AE CRF and assessed by the investigator using the AE intensity grading scale as detailed in [Section 10.2.3](#).

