### 2.1. Modifications to the Analysis Plan Described in the Protocol

There is no change in analysis from the plan specified in the protocol.

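### SAP 3.1.3.2 places a fever of exactly 38.4°C in both the mild and the moderate grade and writes the Fahrenheit threshold as >100.4°F; the protocol has >38.4°C and ≥100.4°F, and the SAP declares no change.

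*SAP*

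**What the plan says.** **SAP 3.1.3.2** defines fever as >100.4°F, with ≥38.0°C in brackets. It then says "For reporting purposes, fever will be analyzed using the following temperature ranges" and lists mild as ≥38.0 to 38.4°C, moderate as ≥38.4 to 38.9°C, severe as >38.9 to 40.0°C and Grade 4 as >40.0°C. Earlier in the same section it says "The grading scale for systemic events is provided in the protocol".

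**Protocol 8.3.4.4** defines fever as ≥38.0°C (≥100.4°F). Table 4 gives mild as ≥38.0 to 38.4°C (100.4 to 101.1°F) and moderate as ">38.4°C to 38.9°C (101.2-102.0°F". Severe and Grade 4 have the same Celsius limits as in the SAP. Readings are recorded to one decimal place, and Fahrenheit readings are to be "programmatically converted to degrees Celsius and then categorized during analysis".

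**SAP 2.1** states: "There is no change in analysis from the plan specified in the protocol".

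**The concern.** A grading rule should send each reading to exactly one grade. As written, the SAP sends 38.4°C to two, and participants can enter that value because temperature is kept to one decimal. The protocol puts the same reading in mild only. The SAP's fever definition also disagrees with itself at 100.4°F, which is fever by its Celsius limit and not fever by its Fahrenheit limit.

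Systemic events, including fever, are a primary safety endpoint in both substudies and are reported by maximum severity (Protocol Tables 5 and 8). The SAP plots maximum severity in its main reactogenicity analysis (6.1.3.1) and repeats it in two sensitivity analyses (6.1.3.3). SAP 3.1.3.2 is therefore the text a programmer will code from. Two programmers could each follow the documents and grade the same reading differently.

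**Working it through.** **1. Conversion.** With C = (F − 32) × 5/9:

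| °F | °C | Grade in Table 4's Fahrenheit column |
|---|---|---|
| 100.4 | 38.000 | mild (lowest value) |
| 101.1 | 38.389 | mild (highest value) |
| 101.2 | 38.444 | moderate (lowest value) |
| 102.0 | 38.889 | moderate (highest value) |
| 102.1 | 38.944 | severe (lowest value) |
| 104.0 | 40.000 | severe (highest value) |

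This reproduces the protocol's pairing of 38.0°C with 100.4°F exactly. It also shows that Table 4's Celsius and Fahrenheit limits agree when the converted value is not rounded.

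**2. Celsius entries.** There are (40.0 − 38.0)/0.1 + 1 = 21 one-decimal values from 38.0 to 40.0°C. Each was graded under both sets of ranges.

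| Reading | Protocol Table 4 | SAP 3.1.3.2 |
|---|---|---|
| 38.4°C | mild | mild and moderate |
| the other 20 values | one grade | the same grade |

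**3. Fahrenheit entries, converted and not rounded.** There are (104.0 − 100.4)/0.1 + 1 = 37 one-decimal values from 100.4 to 104.0°F. None disagrees with Table 4's Fahrenheit column. None reaches the SAP overlap, because 38.4°C is 38.4 × 9/5 + 32 = 101.12°F, which is not a one-decimal reading.

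**4. The >100.4°F sign.** A reading of exactly 100.4°F converts to 38.0°C and is fever under the Celsius limit in both documents. It is lost only if >100.4°F is applied to the raw reading.

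**5. Secondary check: rounding.** Neither document says whether the converted value is rounded before grading. Suppose it were rounded to one decimal:

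- 101.2°F becomes 38.4°C and falls from moderate to mild under Table 4's Celsius limits.
- 102.1°F becomes 38.9°C and falls from severe to moderate under the same limits.
- 101.1°F and 101.2°F both become 38.4°C and enter the SAP overlap.

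So 2 of 37 values would sit one grade below Table 4's Fahrenheit column, and 2 of 37 would be ambiguous under the SAP.

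All of these are counts of possible readings, not of participants.

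**The case against.** The strongest case is that this is a transcription slip of almost no consequence.

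- **Size.** A 38.4°C reading matters only if it was entered in Celsius and sets the participant's highest fever grade over the 7 days. Even then it moves one person between two rows of a descriptive table. This stands, and it limits the weight of the point.
- **Fahrenheit sign.** The protocol converts to Celsius before grading, and the SAP's bands are in Celsius only, so the >100.4°F sign should change nothing. This also stands. The 38.4°C overlap does not depend on it.
- **Rounding.** No text introduces a rounding step, and converting then grading as written reproduces Table 4. That is fair, so rounding is a secondary clarification here.
- **Reference to the protocol scale.** The SAP sentence could mean Table 3, which carries the systemic-event title and omits fever, or it could cover Table 4 as well. If it covers Table 4, the SAP names one scale and prints another. If it means Table 3 only, SAP 2.1 still declares no change. The overlap inside the SAP's own bands remains under both readings.
- **Precedence.** Protocol Section 9 and SAP Section 2 let the SAP modify the protocol. Giving the SAP precedence does not help, because its two bands still share 38.4°C.
- **Highest-grade rule.** It chooses between the e-diary and the AE CRF, and across days. It is not stated as a tie-break for one reading that fits two bands. Used that way, it would give moderate, against Table 4.

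Table 4's footnote on who may assign Grade 4 also differs from the SAP's use of e-diary values above 40.0°C. That is a separate matter.

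**Conclusion.** The concern holds. SAP 3.1.3.2 is not a usable rule at 38.4°C, and it departs from Protocol Table 4 while SAP 2.1 says nothing has changed. The ambiguity covers 1 of 21 recordable Celsius values and, without rounding, 0 of 37 Fahrenheit values. It is confined to the mild/moderate split of a descriptive primary safety endpoint. The noninferiority tests and the sample size are unaffected. The documents give no temperature distribution, so the number of participants affected cannot be estimated. The conclusion rests on two comparison signs in text extracted from a PDF. Both signs appear distinctly within the same SAP section, which makes an extraction error unlikely but does not rule it out.

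**What to change.** First check the two symbols against the signed SAP. If they stand, bring SAP 3.1.3.2 into line with the protocol scale that SAP 2.1 says is unchanged, for analysis grading only:

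- fever: ≥38.0°C (≥100.4°F)
- mild: ≥38.0 to 38.4°C
- moderate: >38.4 to 38.9°C
- severe and Grade 4 temperature limits: as now

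Add one sentence: *Fahrenheit entries are graded on the unrounded converted Celsius value.* This reproduces Table 4's Fahrenheit column at every one-decimal reading from 100.4 to 104.0°F.

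The cost is two symbols and one sentence in the SAP, best made before programming. Data collection and sample size do not change.

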### **3.1.3.3. Adverse Events and Serious Adverse Events**

Standard algorithms for handling missing AE dates and missing AE severity will be applied as described in the Pfizer vaccine data standard rules. Completely missing AE start dates will not be imputed.

The following derivations will be included for each participant:

1. Any AE reported through 1 month after the last vaccination – If the AE started on the same day of the first vaccination, and if the AE start time is before the vaccination time, this AE would not be counted. Otherwise, if the AE start time is missing or after the vaccination time, the AE is included. Any AE reported 1 month after the last vaccination will not be included in the analysis.
2. Any related AE reported through 1 month after the last vaccination – Similar to the above except only a related AE is included (but excluding related reactogenicity reported within 7 days after vaccination).
3. Any immediate AE (AE start time is within 30 minutes after vaccination) reported after each (and any, if applicable) vaccination – Only include AEs that started on the same day of the vaccination and with nonmissing AE start time that is within 30 minutes of the vaccination. If the immediate AE is a related reactogenicity event, this would not be included as an immediate AE.
4. Any severe or life-threatening AE reported through 1 month after the last vaccination.
5. Any AE leading to study withdrawal after vaccination.
6. Any NDCMC reported throughout the study.
7. Any SAE reported throughout the study (including reactogenicity reported in the AE CRF during the e-diary collection period).
8. Any AESI reported throughout the study.

Any AE reported before the first vaccination will not be included in the derivation.

Variables 1 through 5 listed above will be derived with 2 approaches: excluding any reactogenicity (but not excluding reactogenicity SAEs) reported in the AE CRF during the e-diary collection period, and with no exclusion at all.

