7. DISCONTINUATION OF STUDY INTERVENTION AND PARTICIPANT DISCONTINUATION/WITHDRAWAL

7.1. Discontinuation of Study Intervention

Substudy A is a single-dose substudy; therefore, this section is not applicable to that substudy.

Substudy B: It may be necessary for a participant to permanently discontinue study intervention. Reasons for permanent discontinuation of study intervention include the following: AEs, participant request, investigator request, and protocol deviation (including no longer meeting all the inclusion criteria or meeting 1 or more exclusion criteria).

Discontinuation of study intervention does not represent withdrawal from the study. If study intervention is permanently discontinued, the participant should remain in the study to be

evaluated for safety and, where applicable, immunogenicity. See the [SoA](#) for data to be collected at the time of discontinuation of study intervention and follow-up for any further evaluations that need to be completed.

In the event of discontinuation of study intervention, it must be documented on the appropriate CRF/in the medical records whether the participant is discontinuing further receipt of study intervention or also from study procedures, further study follow-up, and/or future collection of additional information.

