8.4.1. Time Period and Frequency for Collecting AE and SAE Information

The time period for actively eliciting and collecting AEs and SAEs (“active collection period”) for each participant begins from the time the participant provides informed consent, which is obtained before the participant’s participation in the study (ie, before undergoing any study-related procedure and/or receiving study intervention), through and including approximately 1 month following the last administration of the study intervention, and AESIs, NDCMCs, and SAEs will be collected from informed consent throughout study participation. In addition, AEs occurring up to 48 hours after blood draws that are related to study procedures will be collected.

Follow-up by the investigator continues throughout the active collection period and until the AE or SAE or its sequelae resolve or stabilize at a level acceptable to the investigator.

When a clinically important AE remains ongoing at the end of the active collection period, follow-up by the investigator continues until the AE or SAE or its sequelae resolve or stabilize at a level acceptable to the investigator and Pfizer concurs with that assessment.

For participants who are screen failures, the active collection period ends when screen failure status is determined.

If the participant withdraws from the study and also withdraws consent for the collection of future information, the active collection period ends when consent is withdrawn.

If a participant permanently discontinues or temporarily discontinues study intervention, or discontinues from the study, because of an AE or SAE, the AE or SAE must be recorded on the CRF and the SAE reported via PSSA or using the Vaccine SAE Report Form.

Investigators are not obligated to actively seek information on AEs or SAEs after the participant has concluded study participation. However, if the investigator learns of any SAE, including a death, at any time after a participant has concluded study participation, and they consider the event to be reasonably related to the study intervention, the investigator must promptly report the SAE to Pfizer via PSSA or using the Vaccine SAE Report Form.

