10.8.6.1.1. Administration

Participants will receive 2 doses of study intervention in accordance with the substudy's SoA. For other details regarding study intervention administration, see [Section 6.1.1](#). The study intervention will be administered into the deltoid muscle, preferably of the nondominant arm, unless medically contraindicated, in which case the injection may be administered in the dominant arm.

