##### 6.1.4.2. Supplementary Analysis

To support the assessment of AEs, the endpoints below, as specified in [Section 3.1.3.3](#), will be summarized with the same analysis population using the same presentation as specified in the main analysis:

- Immediate AEs after each (and any, if applicable) vaccination
- Related AEs reported through 1 month after the last vaccination
- Severe or life-threatening AEs reported through 1 month after the last vaccination
- AEs leading to withdrawal from vaccination throughout the study

- NDCMCs reported from vaccination throughout the study
- AESIs reported from vaccination throughout the study

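### For the two-dose Substudy B, SAP 3.1.3.3 and 6.1.4.2 disagree on AE-related withdrawal, and the only derivation given does not count an AE that stops Dose 2 in a participant who stays in the study

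*SAP*

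**What the plan says.** **Protocol.** Substudy B gives two doses: "Participants will receive 2 doses of study intervention in accordance with the substudy's SoA" (10.8.6.1.1). Section 7.1 applies to Substudy B only and lists AEs first: "Reasons for permanent discontinuation of study intervention include the following: AEs, participant request, investigator request, and protocol deviation". It then separates that outcome from leaving the study, "Discontinuation of study intervention does not represent withdrawal from the study", and says the participant should stay for safety and, where applicable, immunogenicity evaluation. Section 8.4 asks the investigator to establish whether an event made the participant stop study intervention. Section 8.4.1 requires the AE to be recorded on the CRF in these circumstances: "If a participant permanently discontinues or temporarily discontinues study intervention, or discontinues from the study, because of an AE or SAE".

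**SAP.** Section 3.1.3.3 serves both substudies and lists eight AE variables. Variable 5 is "Any AE leading to study withdrawal after vaccination". None of the eight is an AE leading to discontinuation of study intervention. Section 6.1.4.2 begins "To support the assessment of AEs, the endpoints below, as specified in" and then points to 3.1.3.3. Its list includes "AEs leading to withdrawal from vaccination throughout the study" and, directly after it, "NDCMCs reported from vaccination throughout the study". For Substudy B, section 6.5.2 tabulates how many were vaccinated at each dose and how many withdrew after each dose. It also gives reasons for withdrawal and reasons for exclusion from the evaluable and mITT populations.

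**The concern.** In a single-dose study, leaving the study is the only kind of discontinuation, so variable 5 is enough for Substudy A. In Substudy B the protocol creates a second kind: vaccination stops but follow-up continues. The SAP has a derivation for the first kind and, at most, a label for the second.

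Substudy B is the only part of the study that gives a second dose, and describing safety is one of its primary objectives. How often an AE kept someone from completing the two-dose schedule is something a reader of the safety report would expect to find. A programmer who follows 3.1.3.3 as written would fill the 6.1.4.2 row with study withdrawals. The row would then carry a label about vaccination over a count of something else, and it could show no AE-related discontinuation when vaccination had in fact been stopped for AEs.

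**Working it through.** The plan states no figure on this point, so there is none to reproduce. The check is mainly textual.

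**1. One participant traced through the plan.** Take a Substudy B participant who has an AE after Dose 1, is not given Dose 2 because of it, and completes follow-up.

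- Protocol 7.1: study intervention discontinued, not withdrawn from the study.
- SAP 3.1.3.3, variable 5: scored no, because the participant did not leave the study.
- SAP 3.1.3.3, other variables: the AE counts under variable 1 if it starts within 1 month of the last dose received, and under the related, severe, NDCMC, SAE or AESI variables where it qualifies.
- A non-serious reactogenicity event entered on the AE CRF is left out of the main AE analysis (6.1.4.1). It belongs to the Dose 1 reactogenicity tables and returns in the all-AE sensitivity analysis (6.1.4.3).
- SAP 6.5.2: the participant is in the Dose 1 count but not the Dose 2 count. Because two doses are required for the evaluable immunogenicity population (SAP 4), the participant also appears among the exclusions. Nothing specified there gives an AE as the reason.

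Both the event and the missed dose are therefore visible, but no specified output connects them.

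**2. The two possible readings of the 6.1.4.2 row.**

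- Withdrawal from further vaccination. Read literally, this covers the participant above, but 3.1.3.3 contains no derivation for it.
- Withdrawal from the study, over the interval from vaccination onward. This fits the cross-reference to 3.1.3.3 and the next two rows (NDCMCs and AESIs), which use the same phrase as a time interval. It does not cover the participant.

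The text favours the second reading but does not settle it. Neither reading gives Substudy B both outcomes with a derivation for each.

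**3. Scale, for illustration.** Inputs: N = 200 (approximate size, Protocol 10.8.4.1); x participants who lose Dose 2 because of an AE and stay in the study (assumed); no AE-related study withdrawals (assumed). The Clopper-Pearson 95% limits are the 0.025 quantile of Beta(x, N − x + 1) and the 0.975 quantile of Beta(x + 1, N − x). For x = 0 the upper limit is 1 − 0.025^(1/200) = 1.83%.

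| x | Variable 5 as derived | AE leading to Dose 2 not given |
|---|---|---|
| 1 | 0/200, 0% (0 to 1.83%) | 0.5% (0.01 to 2.75%) |
| 2 | 0/200, 0% (0 to 1.83%) | 1.0% (0.12 to 3.57%) |
| 4 | 0/200, 0% (0 to 1.83%) | 2.0% (0.55 to 5.04%) |
| 10 | 0/200, 0% (0 to 1.83%) | 5.0% (2.42 to 9.00%) |

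The chance that at least one of 200 participants falls in the gap is 1 − (1 − p)^200. For an assumed true rate p of 0.5%, 1%, 2% or 5% this is 63%, 87%, 98% or more than 99.9%.

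**The case against.** The strongest reply is that 6.1.4.2 already names withdrawal from vaccination, so the SAP does intend to report these participants and the fault is a loose phrase in 3.1.3.3. Part of this stands. The SAP cannot be said to have settled on omitting them; what can be shown is an inconsistency. But the only derivation is for study withdrawal, and 6.1.4.2 adopts it by reference, so the literal label does not close the gap.

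A reader might go further and infer that the AE disappears from the safety report. The documents do not support that: as traced above, the event is still counted under other AE or reactogenicity variables. A reader might also infer that a missed Dose 2 cannot be seen. It can, in the per-dose counts and the evaluable-population exclusions, and the listings in 6.5.2 are not a closed set. Nor is it a defect that the Dose 2 safety and e-diary populations contain only Dose 2 recipients. Dose 2 rates need that denominator, and the Dose 1 population keeps those who stopped.

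It is also fair to say that the row is a supplementary summary in a descriptive substudy, that discontinuation of vaccination is not a listed primary safety endpoint, and that the SAP treats safety analysis as generally exploratory. No estimand or hypothesis test changes. That limits the weight of the point but is no reason to leave a mislabelled row.

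Finally, Protocol 7.1 lets the discontinuation be documented on the CRF or in the medical records, and the CRF is not among the documents. That the database links the AE to the missed dose is plausible but unverified.

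**Conclusion.** The point holds as an inconsistency between SAP 3.1.3.3 and 6.1.4.2 that matters only in Substudy B. Followed as written, the derivation does not count an AE-stopped Dose 2 as an AE-related discontinuation when the participant remains in follow-up, although the protocol treats that outcome as distinct and asks for it to be documented. What is lost is the link between the AE and the missed dose, not either fact on its own.

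The size is unknown. The range of 1.0% to 5.0% against a reported 0% rests on an assumed 2 to 10 of 200 affected, on none of them leaving the study, on no other AE-related study withdrawals, and on the row being programmed from 3.1.3.3. The documents give no expected rate, so these figures show what the row could hide and are not a forecast. The correction should be made because it is specific and cheap. Confidence is high for the inconsistency, and lower for how the row would actually be programmed.

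**What to change.** - **SAP 3.1.3.3, Substudy B:** replace variable 5 with two variables: (a) AE leading to study withdrawal; (b) AE leading to discontinuation of study intervention, meaning Dose 2 not given. Use the Dose 1 safety population as denominator. Derive both under the two approaches already set for variables 1 to 5 (with and without reactogenicity from the AE CRF), so that a Dose 1 reaction that stops vaccination is not dropped from every version of (b).
- **SAP 6.1.4.2:** list (a) and (b) as separate rows and remove the ambiguous wording.
- **SAP 6.5.2:** for Substudy B, tabulate reasons for not receiving Dose 2, with AE as one of them.
- **Check first:** confirm that the CRF links the AE to the missed dose. Protocol 7.1 and 8.4.1 already require the AE and the discontinuation to be documented.

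The cost is SAP wording, one extra row in the AE table and a reasons breakdown in the disposition table. If the CRF link exists, no new data are needed. No clinical rule changes, and Substudy A needs no change.
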